7.2.3.3 Supplementary Analyses

Supplementary analyses will be conducted for the primary endpoint using the Supplementary 1 estimand strategy.

7.2.4 Secondary objective analyses

Descriptive statistics will be provided for the proportion of patients responding to UACR. An adjusted multiple imputation method will be used for missing UACR measurements, after which the response variables will be determined. As a sensitivity analysis, patients missing Week 14 data will be imputed as non-responders.

All secondary endpoints will be displayed for all patients and with each background medication separately.

7.2.6 Safety analyses

Adverse events will be coded using the Medical Dictionary for Drug Regulatory Activities (MedDRA). Standard BI summary tables and listings will be produced. All adverse events with an onset between start of treatment and end of the REP, a period of 7 days after the last dose of trial medication, will be assigned to the on-treatment period for evaluation.

All treated patients will be included in the safety analysis based on their actual treatments. In general, safety analyses will be descriptive in nature and will be based on BI standards. No hypothesis testing is planned.

Statistical analysis and reporting of adverse events will concentrate on treatment-emergent adverse events, i.e. all adverse events occurring between start of treatment and end of the REP. Adverse events that start before first drug intake and deteriorate under treatment will also be considered as 'treatment-emergent'. Adverse events will be summarised by the treatment at which the subject was randomised, and the treatment at the onset of AE for the drug-related AE.

Frequency, severity, and causal relationship of adverse events will be tabulated by system organ class and preferred term after coding according to the current version of the Medical Dictionary for Drug Regulatory Activities (MedDRA).

Summary of participants with down-titration due to AE will be provided separately. Adverse event of special interest (AESI) and other specific AEs with collection of additional information in the eCRF (which include hyperkalaemia) will be summarised as well. Analysis of serum potassium will further include change from baseline, the incidence of serum potassium levels of 5.6 mmol/L or higher and higher than 6.0 mmol/L.

Laboratory data will be analysed both quantitatively as well as qualitatively. The latter will be done via comparison of laboratory data to their reference ranges. Values outside the reference range as well as values defined as clinically relevant will be summarised. Treatment groups will be compared descriptively with regard to distribution parameters as well as with regard to frequency and percentage of patients with abnormal values or clinically relevant abnormal values.

Vital signs, physical examinations, or other safety-relevant data observed at screening, baseline, during the course of the trial and at the end-of-trial evaluation will be assessed with regard to possible changes compared to findings before start of treatment.

Further details will be provided in the TSAP.

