An individual patient will permanently discontinue BI 690517 / placebo if:

1. The patient's serum potassium measures ≥ 6.0 mmol/L by central or any local laboratory, or ≥ 5.6 mmol/L if down-titration is considered inappropriate.

¹ Where the eGFR drop occurs before the start of BI 690517 / placebo in the Treatment Period (i.e., at Visit 5), but the result is not available until after the patient starts BI 690517/placebo treatment, the patient must still permanently discontinue all randomised study treatment, including BI 690517 / placebo.

2. The patient develops Cushing's syndrome, adrenal insufficiency (including cortisol level $<18 \mu\text{g/dL}$ 30 min (± 5 min) after ACTH application) or the patient's cortisol level is $< 3 \mu\text{g/dL}$ (82.8 nmol/L) at any point in the trial. The patient must be followed according to local guidelines until resolution of the event and the event is going to be reported to the sponsor (see [section 5.2.6.1.4](#)).

An individual patient will permanently discontinue empagliflozin / placebo if:

1. Ketoacidosis is suspected.
2. Fournier's gangrene is suspected.

If empagliflozin / placebo is permanently discontinued during the Randomised Run-In period, the patient should permanently discontinue the trial. If one of the study medications (either empagliflozin/placebo or BI 690517/placebo) is permanently discontinued during the Treatment Period / after the second randomisation at Visit 5, the patient may continue to receive treatment with the other study medication and should continue with scheduled study visits according to the [Flowchart](#).

Treatment interruption

In the following case, all randomised study medication must be interrupted:

- severe SARS-COV-2 infection

In the following cases, the empagliflozin / placebo must be interrupted:

- complicated UTI
- symptomatic volume depletion

In the following cases, the BI 690517 / placebo must be interrupted:

- serum potassium $\geq 5.6 \text{ mmol/L}$ (see [section 4.2.1.1](#))
- serum potassium $\geq 5 \text{ mmol/L}$ if the patient is unable or unwilling to return to the investigational site (see [section 4.2.1.1](#))

In these cases, trial treatment could be restarted upon recovery if medically justified, please see [section 4.1.4](#).

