4.2.1.1 Management of serum potassium elevation

Increased potassium levels are not uncommon in patients with CKD and are often multifactorial in nature. A rise in serum potassium under treatment with BI 690517 cannot be excluded and therefore regular measurements of potassium levels are an integral part of the

visit schedule. For any episode of increased potassium level above 5.0 mmol/L, a clinical evaluation should be performed to make individual treatment decisions if a prompt intervention is required. For BI 690517 the dose might be adjusted to keep potassium levels in an acceptable range. The investigator should consider whether a down-titration is appropriate from a clinical perspective considering symptoms, relevant ECG changes, dynamics of potassium changes, intercurrent disorders, and lower ranges of eGFR. For detailed guidance on how to manage serum potassium elevations, please refer to [Table 4.2.1.1: 1](#).

Table 4.2.1.1: 1 Management of serum potassium

Serum Potassium	Actions (BI 690517 / placebo)
< 5.0 mmol/L	Continue on current dose if deemed appropriate (e.g. in absence of clinical symptoms or slow/small increase over time) For clinically relevant serum potassium increases to < 5.0 mmol/L, the investigator may consider interruption and/or down-titration of BI 690517 /placebo.
≥ 5.0 to <5.6 mmol/L	Option 1: Continue on current dose. Recheck K ⁺ within 72 hours. If levels continue to be ≥5.0 mmol/L, either continue dose with weekly monitoring, or follow Option 2 or Option 3. OR Option 2: Down-titration If down titration is deemed appropriate, the BI 690517 / placebo should be temporarily stopped and the next lower dose will be allocated by IRT as soon as possible. After restarting on a lower dose, investigator should recheck K ⁺ within 72 hours. If levels continue to be >5.0 mmol/L, permanently discontinue. OR Option 3: If down titration is considered inappropriate, permanently discontinue BI 690517 / placebo
≥ 5.6-< 6.0 mmol/L	Option 1: Interruption followed by down titration Study medication should be temporarily interrupted. Investigator should recheck K ⁺ every 72 hours and can restart study medication at the next lower dose once K ⁺ falls to < 5.0mmol/L. After restarting on a lower dose, investigator should recheck K ⁺ within 72 hours. If levels continue to be >5.0, permanently discontinue. OR Option 2: If down titration is considered inappropriate permanently discontinue BI 690517 / placebo

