≥ 6.0 mmol/L	Discontinue BI 690517 / placebo permanently.

In case of symptomatic hyperkalaemia initiation of potassium lowering treatment might be considered as medically indicated, like diuretics, potassium binding resins or other treatments as described in local or global guidelines for treatment of hyperkalaemia.

If BI 690517 or matching placebo must be permanently discontinued due to raised serum potassium, the patient may still continue to receive empagliflozin / matching placebo (see [section 3.3.4](#)).

In the event of elevated potassium ≥ 5 mmol/L, if the patient is unable or unwilling to return to the investigational site, for example during pandemic situation, the BI 690517 or matching placebo should be temporarily interrupted until the patient can return to the investigational site.

For patients taking potassium supplements, serum potassium should be monitored closely, and if serum potassium is ≥ 4.5 mmol/L, the investigator should consider reducing or discontinuing the potassium supplements, according to investigator judgement.

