6.3 SUBJECT SETS ANALYSED

In addition to the subject sets for statistical analysis defined in the CTP, Section 7.2.1, the following subject sets will be used:

Run-in Randomised Set (RIRS):

This patient set includes all randomised patients of the Run-in Period, regardless of being treated or not.

Run-in Treated Set (RITS):

This patient set includes all randomised patients of the Run-in Period who were documented to have taken at least one dose of empagliflozin or placebo.

Full Analysis Set (FAS):

[figure not shown]
This patient set includes all randomised patients who had at least one baseline measurement of UACR at week -2, -1, or 0 and at least one post-baseline measurement when patients are still on treatment of BI 690517. The FAS will be the main analysis set for the analysis of efficacy.

[Table 6.3: 1](#) illustrates the data sets which are to be used for each category class of endpoints.

Table 6.3: 1 Subject sets analysed

Class of endpoint	ES	RIRS	RITS	RS	TS	FAS	PKS
Disposition	X			X			
Exposure / Compliance			X		X		
iPDs				X			
Demographic/baseline		X		X			
Primary endpoint						X	
Secondary endpoint						X	
Other safety/tolerability			X		X		
Further endpoints						X *	
Further PK endpoints							X

* Analyses on further endpoints such as serum potassium, vital signs, and body weight, are based on TS.

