7.8.2 Laboratory data

The analyses of laboratory data will be descriptive in nature and will be based on BI standards "Handling, Display and Analysis of Laboratory Data" (11). Note that data from the central laboratory will be used for all displays described below, unless otherwise specified.

The analysis of continuous laboratory parameters will be based on normalised values, which means transforming to a standard unit and to a standard reference range. The last assessment before the second randomisation at visit 5 is chosen as the baseline value. The laboratory data at EoT visit are defined as EoT values. In the case that the patient is permanently discontinued BI 690517, but is continuing on empagliflozin during Treatment Period, EoT for analysis of laboratory data will be defined as the nearest scheduled lab visit on treatment of BI 690517.

Descriptive statistics of laboratory values over time and for the difference from baseline (see Section 6.7) will be based upon normalised values and provided by visit, including summaries of the last value on treatment, the minimum and maximum value on treatment.

Laboratory values will be compared to their reference ranges; a shift table will be provided for the number of patients within and outside the reference range at baseline and at the last measurement on treatment. This analysis will be based on standardized laboratory values.

Potentially clinically significant abnormalities will be identified based on BI standard rules which are based on converted values and converted reference ranges using SI lab units. These rules will be listed in the SDL appendix of the CTR. Frequency tables will summarise the number of patients with potentially clinically significant abnormalities.

Patients having an abnormal lab value at baseline will be presented separately. A separate listing will present potentially clinically significant abnormal lab values.

All individual laboratory data will be listed. Values outside the reference range will be flagged. In addition, potentially clinically significant values will be flagged in the listing.

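### The upper potassium reporting category (above 6.0 mmol/L) leaves out readings of exactly 6.0, which already meet the protocol's permanent stopping level

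*Protocol*

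**What the plan says.** **Reporting.** Protocol 7.2.6 says the potassium analysis will include change from baseline and "the incidence of serum potassium levels of 5.6 mmol/L or higher and higher than 6.0 mmol/L". The lower category includes its boundary; the upper one does not. The same section says that "other specific AEs with collection of additional information in the eCRF (which include hyperkalaemia) will be summarised as well", without giving a potassium cut-off for those events.

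**Action rule.** Protocol 3.3.4.1 requires permanent discontinuation of BI 690517 or its placebo when "serum potassium measures ≥ 6.0 mmol/L by central or any local laboratory". Table 4.2.1.1: 1 agrees. Its second-highest band is "≥ 5.6-< 6.0 mmol/L", so 6.0 itself falls in the top row, where the action is "Discontinue BI 690517 / placebo permanently".

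**SAP.** Section 6.3 places potassium among the further endpoints: "Analyses on further endpoints such as serum potassium, vital signs, and body weight, are based on TS". Section 7.8.2 adds: "Note that data from the central laboratory will be used for all displays described below", unless otherwise specified. The SAP text available for review states no potassium cut-off.

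**The concern.** One number, 6.0 mmol/L, is used with two different boundaries. The rule that stops treatment includes 6.0, and the summary that reports how often high potassium occurred excludes it. The 5.6 cut-off is inclusive in both places, and no reason is given for treating 6.0 differently.

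Potassium increase is the first BI 690517 risk listed in Table 1.4.2:1, and Protocol 4.1.2 gives it as a reason for testing 20 mg rather than 40 mg. Section 7.2.3 says the target dose is to be estimated with safety taken into account. A reader comparing dose groups will want to know how many patients in each group reached the potassium level at which the protocol requires a permanent stop. Neither planned count answers that: the lower category is too wide, and the upper one is too narrow whenever a patient's highest value is exactly 6.0. The stopping rule could add to this, because a patient stopped at 6.0 may be less likely to record a later on-treatment value above 6.0.

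**Working it through.** The plan states no figure to reproduce. The check has two parts.

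**1. Thresholds side by side**, at each 0.1 mmol/L step around the boundary. The two reporting columns come from Protocol 7.2.6 and the last column from 3.3.4.1 and Table 4.2.1.1: 1.

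| Reading (mmol/L) | In 5.6-or-higher count | In above-6.0 count | Meets permanent stop level (≥ 6.0) |
|---|---|---|---|
| 5.5 | no | no | no |
| 5.6 to 5.9 | yes | no | no |
| **6.0** | **yes** | **no** | **yes** |
| 6.1 to 6.3 | yes | yes | yes |

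From 5.5 to 6.3 the upper category and the stopping level disagree at one value, 6.0. With the category set to ≥ 6.0 they disagree at none.

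**2. How much of the category one boundary value could hold.** The documents give no potassium mean, SD or reporting precision, so every input here is an assumption: normally distributed single readings, reported to 0.1 mmol/L, mean μ from 4.5 to 5.0 and SD σ from 0.4 to 0.6. A reported 6.0 then covers true values from 5.95 to 6.05.

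- P(reported ≥ 6.0) = 1 − Φ((5.95 − μ)/σ)
- P(reported exactly 6.0) = Φ((6.05 − μ)/σ) − Φ((5.95 − μ)/σ)
- Share exactly 6.0 = second line ÷ first line

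For example, with μ = 4.7 and σ = 0.5 the standardised limits are (5.95 − 4.7)/0.5 = 2.5 and (6.05 − 4.7)/0.5 = 2.7. The tail areas are 0.00621 and 0.00347, the difference is 0.00274, and the share is 0.00274/0.00621 = 0.44.

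| Mean | SD | P(≥ 6.0) | P(exactly 6.0) | Share exactly 6.0 |
|---|---|---|---|---|
| 4.5 | 0.4 | 0.0001 | 0.0001 | 0.63 |
| 4.5 | 0.5 | 0.0019 | 0.0009 | 0.48 |
| 4.5 | 0.6 | 0.0078 | 0.0029 | 0.38 |
| 4.7 | 0.4 | 0.0009 | 0.0005 | 0.58 |
| 4.7 | 0.5 | 0.0062 | 0.0027 | 0.44 |
| 4.7 | 0.6 | 0.0186 | 0.0064 | 0.34 |
| 5.0 | 0.4 | 0.0088 | 0.0044 | 0.51 |
| 5.0 | 0.5 | 0.0287 | 0.0109 | 0.38 |
| 5.0 | 0.6 | 0.0567 | 0.0166 | 0.29 |

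Shares are taken from unrounded values. They run from 29% to 63%. In absolute terms, readings of exactly 6.0 run from about 0.1 to about 17 per 1,000 readings. The largest shares go with the rarest events.

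**The case against.** The strongest reply is that this is one boundary value in one descriptive row, and that readings of 6.0 are not lost. They are in the 5.6-or-higher count, in the individual laboratory listings and in the summaries of the maximum on-treatment value (SAP 7.8.2). If reported as adverse events, they can also appear in the hyperkalaemia and discontinuation tables of SAP 7.8.1. All of that stands, and it is why the point is small. It does not supply the missing count, because none of those displays is planned as the number of patients at or above 6.0.

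Four stronger readings are tempting, and the documents do not support them:

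- **That the two reporting cut-offs were meant to copy the action thresholds.** No section says so, and Table 4.2.1.1: 1 also has a boundary at 5.0 that 7.2.6 does not report. A drafting slip is plausible but not shown.
- **That severe hyperkalaemia is under-counted.** The protocol does not define the upper category as severe hyperkalaemia; it gives only a number.
- **That changing the boundary would make the count agree with the discontinuation tables.** It would not. Table 4.2.1.1: 1 also allows permanent discontinuation below 6.0, the stopping rule accepts any local laboratory result while SAP laboratory displays default to central data, and the planned discontinuation tables are based on adverse events.
- **That about half of the affected patients would be missed.** The shares above are per reading and rest on assumed inputs. Patient incidence depends on each patient's highest value over several visits, so the shares do not carry over directly.

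The SAP may also already state a suitable cut-off. Protocol 7.2.6 leaves further detail to it, and its further-endpoint sections are not in the text available for review. The finding is therefore made against Protocol 7.2.6 only.

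**Conclusion.** The inconsistency is present in the current protocol text and is minor. A highest reading of exactly 6.0 mmol/L meets the laboratory stopping level in 3.3.4.1 and Table 4.2.1.1: 1 but is outside the upper category in 7.2.6, so neither planned incidence gives the number of patients who reached that level. This follows from the wording alone and needs no distributional assumption.

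Its size does need assumptions. Under the stated normal model the boundary value could be a sizeable part of a rare category while adding few readings in absolute terms; if no patient peaks at exactly 6.0, nothing changes. No hypothesis test is planned on safety data, and the primary analysis, type I error and power are unaffected. The reason to act is that the row describes the main mechanism-related risk by dose group and the correction is nearly free.

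**What to change.** In Protocol 7.2.6, report the incidence of serum potassium at or above 6.0 mmol/L, either in place of the above-6.0 category or next to it. Use the same boundary in the SAP potassium display if it is not already there. This aligns a reporting category with a threshold the protocol already contains; it neither changes nor endorses any clinical rule.

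A footnote to the display could say that the count is based on central laboratory values (if the SAP default applies) and is not expected to equal the number of discontinuations.

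The cost is one inequality sign or one extra table row, with no new data. The reported upper incidence can only stay the same or rise.

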7.2.7 Other Analyses

Details on the further analyses will be described in TSAP if needed.

7.2.8 Interim Analyses

No interim analysis is planned but a Data Monitoring Committee (DMC) will be in place with tasks as described in [section 8.7](#).

7.3 HANDLING OF MISSING DATA

In the primary analysis of continuous endpoints, missing data will not be imputed. As a sensitivity analysis, missing UACR data will be imputed using an adjusted multiple imputation model (refer to [Section 7.2.3.1](#)). Data from this multiple imputation will be used to compute responder endpoints.

Missing or incomplete AE dates will be imputed according to BI standards. Handling of missing data for secondary endpoints as well as for sensitivity analysis will be described in the TSAP.

Handling of missing PK data will be performed according to the relevant internal procedures. PK parameters that cannot be reasonably calculated based on the available drug concentration-time data will not be imputed.

7.4 RANDOMISATION

BI will arrange for the creation of the randomisation scheme and the packaging and labelling of trial medication. Patients will be randomised to double-blind treatment. Approximately equal numbers of patients will be randomised to each treatment group. The randomisation list will be generated using a validated system, which involves a pseudo-random number generator so that the resulting randomisation scheme will be both reproducible and non-

predictable. The block size will be documented in the Clinical Trial Report. Access to the codes will be controlled and documented.

In this study, patients will undergo a 2-step randomisation, with the first randomisation performed prior to the Randomised Run-in and the second randomisation performed prior to the Treatment Period. Patients must fulfil the criteria (as described in [section 3.3.2](#)) in order to be randomised into the Treatment Period. In order to ensure a balance of patients between treatment groups, the trial will use stratified randomisation according to prognostic variables eGFR (< 45 and ≥ 45 mL/min/1.73 m²), UACR (≤ 750 and >750 mg/g). At the first step, patients will be randomised to the treatment of empagliflozin or matching placebo in a 1:1 ratio for 8 weeks. At the second step, patients will be randomised to the Treatment Period in a 1:1:1:1 ratio for the treatment of 3 doses of BI 690517 (3 mg QD, 10 mg QD, and 20 mg QD) and matching placebo for 14 weeks, on the top of empagliflozin or matching placebo from the first randomisation.

7.5 DETERMINATION OF SAMPLE SIZE

The sample size calculation is conducted assuming effect size of BI 690517 versus placebo, (0, 0.10, 0.20, 0.35) for (placebo, BI 690517 3 mg, BI 690517 10 mg, BI 690517 20 mg total daily dose) in log transformed UACR measured in morning void urine after 14 weeks of trial treatment from baseline. The pre-specified models in [Figure 7.5: 1](#) are used for testing null hypothesis. The following models have been selected as the candidate set of possible dose response patterns based on current expectation. Assuming the following dose groups will be tested: placebo, active BI 690517 3 mg, 10 mg, and 20 mg in terms of total daily dose.

Emax: 80% of the maximum effect is achieved at 10 mg.

Exponential: 15% of the maximum effect is achieved at 10 mg.

Linear: No assumption is needed.

[figure not shown]

Figure 7.5: 1 Shape of the considered dose response patterns for the MCPMod analysis (dose reflects planned daily dose)

In a scenario with assumed effect of (0, 0.10, 0.20, 0.35) in log (UACR) change from baseline after 14 weeks in the Treatment Period (placebo, BI 690517 3 mg, BI 690517 10 mg, BI 690517 20 mg), the trial will have 89.7% power to detect a non-flat curve using MCPMod considering one-sided 5% alpha with sample size of 60 patients per treatment arm (in patients randomised to placebo during the run-in period).

In a scenario with assumed effect of (0, 0.10, 0.16, 0.22) in log (UACR) change from baseline after 14 weeks in the Treatment Period (placebo, BI 690517 3 mg, BI 690517 10 mg, BI 690517 20 mg), the trial will have 83.1% power to detect a non-flat curve using MCPMod considering one-sided 5% alpha with sample size of 120 patients per treatment arm (all patients combined).

The sample size/power calculation were determined based on 10,000 simulations for the scenario using R4.0.2. To achieve 60 patients per group (480 total patients), 552 patients will be randomised during the Run-in period to account for a dropout rate of at most 15% before the second randomisation. A one-sided alpha of 5% will be used to keep the sample size reasonably low in this Phase 2 trial.

8. INFORMED CONSENT, TRIAL RECORDS, DATA PROTECTION, PUBLICATION POLICY, AND ADMINISTRATIVE STRUCTURE

The trial will be carried out in compliance with the protocol, the ethical principles laid down in the Declaration of Helsinki, in accordance with the ICH Harmonized Guideline for Good Clinical Practice (GCP), relevant BI Standard Operating Procedures (SOPs), the EU directive 2001/20/EC / EU regulation 536/2014, the Japanese GCP regulations (Ministry of Health and Welfare Ordinance No. 28, March 27, 1997) and other relevant regulations. Investigators and site staff must adhere to these principles. Deviation from the protocol, the principles of ICH GCP or applicable regulations as will be treated as “protocol deviation”. Standard medical care (prophylactic, diagnostic and therapeutic procedures) remains the responsibility of the treating physician of the patient.

The investigator will inform the sponsor immediately of any urgent safety measures taken to protect the trial patients against any immediate hazard, as well as of any serious breaches of the protocol or of ICH GCP.

The Boehringer Ingelheim transparency and publication policy can be found on the following web page: trials.boehringer-ingelheim.com. The rights of the investigator and of the sponsor with regard to publication of the results of this trial are described in the investigator contract. As a rule, no trial results should be published prior to finalisation of the Clinical Trial Report.

The certificate of insurance cover is made available to the investigator and the patients, and is stored in the ISF.

